15 SAFETY

15.1 Safety Parameters

The National Cancer Institute Common Terminology Criteria for Adverse Events (NCI-CTCAE; Version 4.03 - www.hrc.govt.nz/sites/default/files/CTCAE%20manual%20-%20DMCC.pdf) will be used for grading toxicities unless otherwise specified. Subjects will be monitored throughout the treatment and follow-up period for occurrence of AEs (acute, delayed, and/or cumulative), as well as for changes in clinical status, vital sign measurements, and laboratory data. Safety parameters to be measured/assessed include vital sign measurements, physical examinations, concomitant medications, hematology, serum chemistries, urinalysis, pregnancy testing, ECGs, and ECOG performance status.

15.2 Adverse Event Definition

An AE is defined as any untoward medical occurrence associated with the use of a drug in humans, whether or not considered drug related. AEs include:

- Suspected adverse drug reactions (abbreviated as either SADR or SAR). This may be serious or not serious;
- Reactions from drug overdose, abuse, withdrawal, sensitivity, or toxicity;
- Significant changes or abnormalities, when compared to baseline, in structure (sign), function (symptom), clinical laboratory results, ECG results, or physiological testing. This includes any worsening of a pre-existing condition temporally associated with the use of study drug;
- Other medical events, regardless of their relationship to the study drug, such as injury, surgery, accidents, extensions of symptoms, or apparently unrelated illnesses.

Findings existing prior to signing informed consent will be recorded as medical history. For the purpose of data collection, all untoward events that occur after informed consent through 30 days after last dose of study treatment are to be recorded on eCRFs by the investigational site. This requirement includes AEs from unscheduled as well as scheduled visits.

An AE does not include:

- Medical or surgical procedures (e.g. surgery, endoscopy, tooth extraction, transfusion); when the condition that leads to the procedure is an AE;
- Pre-existing diseases, or conditions or laboratory abnormalities present or detected prior to the screening visit, those do not worsen;
- Situations where an untoward medical occurrence has not occurred (e.g. hospitalization for elective surgery, social, and/or convenience admissions);
- Overdose of either tesevatinib or a concomitant medication without any signs or symptoms, unless the subject is hospitalized for observation.

15.3 Evaluating Adverse Events

The investigator will determine the seriousness, intensity, and causality of an AE associated with the use of the study drug (i.e., events where there is a reasonable possibility that the event may have been caused by the study drug) based on the definitions that follow.

15.3.1 Serious Adverse Events

(Notify sponsor or designee within 24 hours of first awareness)

The SAE definition and reporting requirements are in accordance with the ICH Guideline for Clinical Safety Data Management, Definitions, and Standards for Expedited Reporting, Topic E2A, with Title 21 Part CFR 312.32, and the Guidance for Industry and Investigators Safety Reporting Requirements for INDs and BA/BE Studies.

SAE: An AE is considered "serious" if, in the view of either the investigator or sponsor, it results in any of the following outcomes:

- **Death:** This includes any death that occurs while the subject is “on study” as well as any death that occurs within 30 days after last dose of study drug administration.

Note: Death is an outcome of an AE, and not an AE in itself. The event(s) that caused death (e.g. illness, accident) is the SAE. Death due to any other cause(s) must also be reported as an outcome of the reportable SAE.

- **Life-threatening adverse event:** An AE or suspected adverse reaction is considered “life-threatening” if, in the view of either the investigator or sponsor, its occurrence places the patient or subject at immediate risk of death. It does not include an AE or suspected adverse reaction that, had it occurred in a more severe form, might have caused death).
- **Inpatient hospitalization or prolongation of existing hospitalization:**

In the absence of an AE, the investigator should not report hospitalization or prolongation of hospitalization. This is the case in the following situations:

- Hospitalization or prolongation of hospitalization is needed for a procedure required by the protocol;
- Hospitalization or prolongation of hospitalization is part of routine procedure followed by study center;
- Hospitalization for survey visits or annual physicals.

In addition, a hospitalization planned before the start of the study for a pre-existing condition which has not worsened does not count as an SAE.

- Persistent or significant incapacity or substantial disruption of the ability to conduct normal life functions;
- Congenital anomaly/birth defect;
- Important medical event: An event that may not result in death, be life threatening, or require hospitalization may be considered serious when, based upon appropriate medical judgment, it may jeopardize the subject and may require medical or surgical intervention to prevent one of the outcomes listed in this definition.

Some serious events will not be reported as SAEs, including:

- Disease progression;
- Death due to disease progression occurring more than 30 days after the last dose of study drugs;
- Medical or surgical procedures when the condition that leads to the procedure is an AE;
- Pre-existing diseases, or conditions or laboratory abnormalities present or detected prior to the screening visit, that do not worsen;
- Situations for which an untoward medical occurrence has not occurred (e.g. hospitalization for elective surgery, social and/or convenience admissions).

15.3.2 Suspected Unexpected Serious Adverse Reaction (SUSAR)

(Notify sponsor or designee within 24 hours of first awareness)

A suspected unexpected serious adverse reaction is any adverse drug event, the specificity or severity of which is not consistent with those noted in the current protocol and/or Investigator's Brochure (IB). This refers to any AE that has not been previously observed (e.g. included in the IB), rather than from the perspective of such an event not being anticipated from the pharmacological properties of the product.

15.3.3 Unexpected Adverse Events

An AE is considered “unexpected” if it is not listed in the Investigator Brochure (IB) or is not listed at the specificity or severity that has been observed; or, if an IB is not required or available, is not consistent with the risk information described in the General Investigational Plan or elsewhere in the current application. Also refers to AEs that are mentioned in the IB as occurring with a class of drugs or as anticipated from the pharmacological properties of the drug, but are not specifically mentioned as occurring with the particular drug under investigation.

15.3.4 Non-Serious Adverse Events

All other AEs, not fulfilling the previous definitions, are classified as non-serious.

15.3.5 Protocol-Related Adverse Events

AEs that are not test drug related may nevertheless be considered by the investigator or the medical monitor to be related to the conduct of the clinical study. That is, the event may be related to the fact that a subject is participating in the study. For example, a protocol-related AE may be an event that occurs during a washout period or that is related to a procedure required by the protocol.

15.3.6 Relationship/Causality to Study Drug

The investigator will attempt to assess the relationship of the event to study drug using a 5- point scale (not related, unlikely-related, possibly related, probably related, or definitely related).

15.3.7 Recording Adverse Events

All AEs (including SAEs) are to be accurately recorded on the Adverse Event page of the subject's eCRF. The date of onset as well as the duration of the event also should be recorded. In addition, the method used to treat the AE and the outcome of the AE also will be noted. The investigator will assess the relationship of the event to study drug (not related, unlikely-related, possibly related, probably related, or definitely related).

15.3.8 Adverse Event Monitoring and Follow-Up

The investigator will follow all subjects who experience AEs until there is a return to the subject's baseline condition, Grade 1 severity or until a clinically satisfactory resolution has been achieved. The appropriate follow-up visits must be scheduled and the specific tests repeated or performed as necessary. Where a diagnosis is possible, it is preferable to report this diagnosis rather than a series of terms (signs/symptoms) relating to the diagnosis.

15.3.9 Laboratory and ECG Abnormalities

For the purposes of grading creatinine, the ULN – not the subject's Cycle 1 Day 1 value - will be used to determine grade.

For the purpose of grading sodium, values of 126–130 mmol/L will be considered to be Grade 2 and values of 120–125 mmol/L will be considered Grade 3.

For the purposes of this study, ECG abnormalities will be handled in the same manner as laboratory abnormalities.

Non-Clinically Significant (NCS) Laboratory Abnormalities

All laboratory results must be filed in the subject's medical record and be monitored. The investigator must review laboratory results in a timely manner demonstrated by signature/date and assignment of clinical significance assessment. Non-clinically-significant laboratory abnormalities, i.e., minor deviations from the normal range, are expected and it is likely that no medical intervention will be required. Such results will not be considered to be AEs.

Clinically Significant (CS) Laboratory Abnormalities

Any laboratory abnormality that is considered to be clinically significant by the investigator will be recorded on the AE eCRF. A clinically significant abnormal test result will be considered an AE if:

- It is not associated with an already reported AE, diagnosis or pre-existing condition;
- There is a change in concomitant medication or intervention as needed, in direct response to the laboratory result;
- The investigator exercises his/her discretion to make significance determinations for any subject laboratory result or result that requires intervention.

All such lab abnormalities will be repeated and assessed by the investigator, or licensed (MD), as soon as possible for "seriousness" and if they meet the regulatory definition of "serious", they will be reported as SAEs following regulatory and protocol requirements. Repeat laboratory tests may be run in order to monitor the result.

Serious Laboratory Abnormalities

Any lab abnormality meeting the regulatory definition of "serious" must be recorded on both the AE eCRF/record and the SAE Form. If a subject experiences a serious toxicity or dies, the FDA will be notified within 24 hours, as required.

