16.3.7 Safety Data

Safety analyses will be performed on all subjects who received any quantity of study drug. AEs that are not related to treatment and that occur more than 30 days after the administration of the last dose of treatment will not be reported or analyzed.

Safety analyses will present results by Cohort and, where appropriate, the three cohorts combined.

Safety observations and measurements include AEs, safety laboratory tests, vital sign measurements, physical examinations, pregnancy status, ECG assessments, and pharmacokinetic data.

Treatment-emergent AEs will be summarized using the Medical Dictionary for Regulatory Activities (MedDRA[®]) (Version 18.1 or higher) System Organ Class (SOC) and preferred term, classified from verbatim terms. The incidence and percentage of subjects with at least 1 occurrence of a preferred term will be included, according to the most severe grade using the National Cancer Institute Common Terminology Criteria for Adverse Events (NCI-CTCAE; Version 4.03). The number of events per preferred term will also be summarized. Causality (relationship to study treatment) will be summarized separately.

AEs, SAEs, related AEs, related SAEs, \geq Grade 3 AEs, related \geq Grade 3 AEs, and AEs leading to withdrawal, dose modification, or treatment discontinuation will be summarized by cohort and tesevatinib overall according to SOC and preferred terms. AEs will also be summarized in listings. Duration of AEs will be determined and included in listings, along with action taken and outcome.

Laboratory results will be classified according to NCI-CTCAE Version 4.03 and summarized by cohort. Laboratory results not corresponding to a coded term will not be graded. Incidence of laboratory abnormalities will be summarized. The worst on-study grade after the first dose of study drug will be summarized. The incidence of \geq Grade 3 laboratory abnormalities under treatment and shifts in toxicity grading from Cycle 1 Day 1 to highest grade post-Cycle 1 Day 1 will be displayed. Results for variables that are not coded will be presented in the listings as below, within, and above the normal limits of the local laboratory.

Vital sign measurements will be summarized at each scheduled time point using descriptive statistics. ECOG performance status results will be summarized by scheduled time point. Additional statistical details will be provided in a prospective statistical plan.

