#### 1.3.2 Safety Assessments

The NCI CTCAE; Version 5 will be used for grading toxicities. Safety assessments will include adverse events (AEs), serious adverse events (SAEs), physical examinations, vital sign measurements, clinical safety laboratory evaluations (hematology, serum chemistry, and urinalysis), Eastern Cooperative Oncology Group (ECOG) scores, and electrocardiograms (ECGs).

The AE reporting period for a subject enrolled in the study begins when the subject provides informed consent and is continued through 30 days after the last dose of

study drug or until start of new treatment. All AEs that occur in enrolled subjects during the AE reporting period specified in the protocol must be recorded, regardless of the relationship of the AE to study drug. Any known untoward event that occurs beyond the AE reporting period that the investigator assesses as possibly related to tesevatinib should be included.

Vital sign measurements, including sitting blood pressure, pulse rate, respiratory rate, and temperature will be monitored throughout the study.

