## 2 Statistical Methods

No formal hypothesis testing will be conducted. Descriptive statistics including 95% confidence intervals for response rate, time-to-event and continuous measurements will be summarized by cohorts.

Tesevatinib concentrations in the plasma and CSF will be summarized at each scheduled collection time point using descriptive statistics, and displayed graphically.

AEs, SAEs, Grade 3&4 AEs, related AEs, related SAEs, related Grade 3&4 AEs, death, and AEs leading to withdrawal, dose modification, or treatment discontinuation will be summarized by cohort and overall according to high level terms (HLT) and preferred terms (PT). Adverse events will also be summarized in listings. Duration of AEs will be determined and included in listings, along with action taken and outcome.

Vital sign measurements will be summarized at each scheduled time point using descriptive statistics. The ECOG performance status results will be summarized by scheduled time point.

Laboratory results will be classified according to NCI-CTCAE Version 4.03 and summarized by cohort. The worst on-study grade after the first dose of study drug will be summarized. The incidence of ≥ Grade 3 laboratory abnormalities under treatment and shifts in toxicity grading from Cycle 1 Day 1 to highest grade post-Cycle 1 Day 1 will be displayed. Results for variables that are not coded will be presented in the listings as below, within, and above the normal limits of the local laboratory.

The table of list of tables, listings, and figures is displayed in Table 1.

 Table 1 Content of efficacy tables

| T/F/L | Number | Title   | Order                        | Population                    | Summary Statistics            |
|-------|--------|---|------------------------------|-------------------------------|-------------------------------|
| T     | 1.1.1  | Response rate by cohort   | Primary efficacy             | All treated subjects          | ORR, CR, PR, exact CI         |
| Т     | 1.1.2  | Response rate by visit and cohort                                   | Primary efficacy             | All treated subjects          | ORR, CR, PR, exact CI         |
| L     | 1.1.1  | Tumor size / symptoms and signs by visit and cohort                 | Primary efficacy             | All treated subjects          |                               |

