## Statistical Analysis Plan

| L | AE  | 6.1.2 | AE Leading to Treatment Discontinuation  | All treated patients |
|---|-----|-------|--|----------------------|
| L | AE  | 6.1.4 | Death  | All treated patients |
| Т | Lab | 7.1.1 | Lab values and their change from baseline by cohort Shifts in toxicity grading from baseline to highest grade post-baseline of | All treated patients |
| T | Lab | 7.1.3 | laboratory abnormalities by cohort   | All treated patients |
| L | Lab | 7.1.1 | Lab values with CTCAE grade >= 3   | All treated patients |
| T | VS  | 8.1.1 | Vital signs and their change from baseline by cohort   | All treated patients |
| L | VS  | 8.1.1 | Vital signs  | All treated patients |
| L | VS  | 8.2.1 | Physical examinations  | All treated patients |
| T | ECG | 9.1.1 | ECG parameters and their change from baseline by cohort  | All treated patients |
| T | ECG | 9.2.1 | QTcF abnormalities by cohort   | All treated patients |
| L | ECG | 9.1.1 | ECG values   | All treated patients |

Abbreviations: AE = adverse event; CNS = central nervous system; CSF = cerebrospinal fluid; CTCAE = Common Terminology Criteria for Adverse Events; DNA = deoxyribonucleic acid; ECG = electrocardiogram; EGFR = epidermal growth factor receptor; HLT = high level terms; MRI = magnetic resonance imaging; NSCLC = non-small cell lung cancer; OS = overall survival; PFS = progression-free survival; TEAEs = treatment-emergent adverse events; VS = vital signs

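### The laboratory analysis sections and the SAP grade by unmodified CTCAE 4.03, leaving out the study-specific sodium and creatinine grading in protocol 15.3.9; separately, the SAP names CTCAE Version 5 in two places

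*Protocol*

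**What the plan says.** Protocol 15.1 names CTCAE 4.03 as the scale that "will be used for grading toxicities unless otherwise specified". Protocol 15.3.9 then specifies otherwise for two tests. For sodium, "values of 126–130 mmol/L will be considered to be Grade 2 and values of 120–125 mmol/L will be considered Grade 3". For creatinine, it is the ULN, and not the subject's "Cycle 1 Day 1 value - will be used to determine grade".

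The sections that define the laboratory output do not carry this over. Protocol 16.3.7 states: "Laboratory results will be classified according to NCI-CTCAE Version 4.03 and summarized by cohort". The synopsis, under Statistical methods, has the same sentence. Both go on to leave ungraded any result without a coded term, but neither mentions sodium or creatinine. SAP Section 2 again says "Laboratory results will be classified according to NCI-CTCAE Version 4.03". It adds that the incidence of Grade 3 or higher abnormalities will be shown and that "shifts in toxicity grading from Cycle 1 Day 1 to highest grade post-Cycle 1 Day 1 will be displayed". SAP Table 2 lists the shift table as T 7.1.3, and L 7.1.1 as "Lab values with CTCAE grade >= 3".

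On the version, SAP 1.3.2 says "The NCI CTCAE; Version 5 will be used for grading toxicities". SAP 1.3.1.1 also mentions Version 5 when describing the Cohort B symptom assessments, then defines symptom improvement and progression by 4.03.

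**The concern.** A programmer works from the SAP. SAP Section 2 gives a complete, operative grading instruction for laboratory results, and nothing in it points to 15.3.9. Followed literally, it produces grades on a scale that the protocol has set aside for sodium and creatinine.

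Creatinine is the test where this matters more. Elevated creatinine is listed in protocol 11.1.3 among the adverse events associated with tesevatinib. Protocol 5.2.1 attributes it to blocked tubular secretion and notes that it may not reflect a change in kidney function. Grading on the ULN alone avoids grading a rise from the subject's own starting value. A shift table that runs from Cycle 1 Day 1 without that rule could show creatinine toxicity that the protocol chose not to grade.

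**Working it through.** The plan states no figure on this point, so there is none to reproduce. The check is a comparison of the rules, with one set comparison for sodium and one line of arithmetic for creatinine.

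1. **Which rule governs.** Protocol 15.1 makes CTCAE 4.03 the default and allows departures. Protocol 15.3.9 is such a departure. Its wording is about grading in general and is not confined to adverse event reporting. It therefore governs sodium and creatinine grades.

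2. **Where the departure is carried over.** The allowance stands in 15.1. Protocol 16.3.7, the synopsis (both Statistical methods and the grading sentence under Safety assessments) and SAP Section 2 contain neither the allowance nor a reference to 15.3.9.

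3. **Whether the sodium scales differ.** The CTCAE cut-offs are not in the documents, so the evidence has to be internal. Protocol 11.1.2 and the synopsis exempt from the mandatory hold Grade 3 sodium values of 126 mmol/L or more in a subject with diarrhea. I read this as low sodium.
   - Grade 3 under 15.3.9: {120, ..., 125}.
   - Exempted values: {126, 127, ...}.
   - Intersection: empty.

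   Under 15.3.9 the exemption can never apply. It has content only on a scale where some low sodium value of 126 or more is Grade 3. So a second sodium scale is in play, and values from 126 upwards in the disputed band are Grade 2 on one and Grade 3 on the other. That this second scale is unmodified CTCAE 4.03 is an inference from the protocol's default; the width of the band is not given.

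4. **Whether the creatinine scales differ.** Protocol 15.3.9 expressly rules out the Cycle 1 Day 1 value, which has a purpose only if grading could otherwise use it. An illustration of direction: protocol 5.2.1 reports a median creatinine rise of 22% from screening at Day 7 in 9 ADPKD subjects on 50 mg, with cystatin C unchanged. A subject who rises 22% stays within the ULN if the start is at or below 1/1.22 = 0.82 of the ULN. On a ULN basis there is then nothing to grade. On a basis that uses the starting value the same subject stands at 1.22 times the start. Whether that earns a grade depends on a cut-off that the documents do not give.

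5. **Which outputs change.**
   - T 7.1.3 (shifts): both tests.
   - L 7.1.1 and the Grade 3 or higher incidence: sodium, by step 3. For creatinine nothing in the documents shows a value moving across the Grade 3 line.

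6. **Version.** The protocol uses 4.03 in the synopsis, 15.1 and 16.3.7. SAP 1.3.2 says Version 5, while SAP Section 2 says 4.03 for laboratory results. This is a contradiction with the protocol and within the SAP, but it is separate from steps 1 to 5.

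**The case against.** The strongest reply is that the protocol already settles the matter. A specific rule modifies a general one, 15.1 says so in terms, and 16.3.7, the synopsis and the SAP merely restate the general rule. On this view all that is missing is a cross-reference.

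That is fair as an account of what the protocol intends, and it keeps the severity low. It does not remove the defect, because the instruction to be programmed is in the SAP and reads as complete. Protocol 16.3.7 also shows that its authors stated an exception where they wanted one, for results with no coded term.

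A reader might infer more than this. Four stronger readings are not supported:

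- **That Grade 3 or higher creatinine counts would change.** Step 5 found no evidence of this.
- **That the creatinine effect can be sized from the ADPKD data.** Those rises were measured from screening, not Cycle 1 Day 1, in a different disease at 50 mg against 300 mg here. Any count would also need an assumed cut-off. If that cut-off is taken anywhere from 1.0 to 1.5 times the starting value, the share of the 9 subjects crossing it could be anything from 0% to 100%.
- **That Version 5 would drive the laboratory tables.** SAP Section 2 names 4.03 for laboratory results, so the three outputs above do not depend on SAP 1.3.2.
- **That the sodium exemption is a dosing hazard.** With diarrhea, a sodium of 126 or more leads to no mandatory hold under 15.3.9 and none under the exemption. Dosing could differ only for a drug-related low sodium in the disputed band without diarrhea, at a site grading by plain CTCAE. The result would be an extra temporary hold. Protocol 11.1.3 already lets the investigator withhold drug for up to 28 days.

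**Conclusion.** Wrong as written, low severity. SAP Section 2, protocol 16.3.7 and the synopsis state a laboratory grading rule that does not match the one the protocol sets for sodium and creatinine. Separately, SAP 1.3.2 and 1.3.1.1 name a CTCAE version that the protocol does not use.

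The consequence is confined to descriptive safety tables. No hypothesis test is planned, and the Cohort B definitions of improvement and progression already name 4.03. How many subjects would be regraded cannot be derived, because neither the CTCAE cut-offs nor the expected sodium and creatinine distributions at 300 mg in this population are given.

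The conclusion rests on two readings: that 15.1 makes 15.3.9 operative for analysis as well as reporting, and that the sodium exemption in 11.1.2 refers to low sodium.

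**What to change.** - In protocol 16.3.7, the synopsis Statistical methods and SAP Section 2, state that laboratory results are graded by NCI-CTCAE Version 4.03 as modified by protocol 15.3.9 for sodium and creatinine, with CTCAE 4.03 cut-offs otherwise retained. State that this applies to T 7.1.3, L 7.1.1 and the Grade 3 or higher incidence.
- Say modified by, not replaced by. Protocol 15.3.9 gives only two sodium bands, nothing below 120 or above 130 mmol/L, and no creatinine cut-offs, so used alone it would leave values without a grade.
- Change Version 5 to Version 4.03 in SAP 1.3.2 and SAP 1.3.1.1.
- In the synopsis Safety assessments, qualify the grading sentence with: unless otherwise specified (see 15.3.9).
- Leave the sodium hold exemption in 11.1.2 and the synopsis as it is. It is redundant under 15.3.9 but harmless, and it guards against a needless hold if a site grades by plain CTCAE.

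The cost is one clause in three places, two version numbers and one qualifier. No new data are needed. It is best done before the laboratory tables are programmed.
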